## 2. Background:

Describe the background information that led to the plan for this project.

The rising incidence of diabetes and obesity has paralleled the increased consumption of not just glucose, but also of fructose in the form of high fructose sweeteners and sucrose, which has been associated with numerous adverse metabolic effects including weight gain, insulin resistance, cognitive decline, and stroke [1-3]. While CNS glucose infusion decreases feeding in rodents, CNS fructose infusion has an opposite effect to promote feeding [4,5], which is due to differential effects on hypothalamic malonyl-CoA [5]. Furthermore, studies in humans have shown that, compared to glucose, fructose ingestion results in lower levels of satiety hormones such as GLP-1 [6] and insulin [7]. Glucose and fructose ingestion also result in distinct patterns of regional cerebral blood flow as assessed by functional MRI [8]. In rodents, high fructose diet results in impaired spatial memory [9,10], and epidemiological data in humans have noted an association between increased fructose consumption and lower score on the mini-mental status exam [11]. Taken together, these studies have generated considerable interest in the possible effects of fructose in the brain.

The polyol pathway is an alternate glucose pathway that bypasses glycolysis [3,4] and is present throughout the human body, including the brain [5,6]. While only a small percentage of glucose enters this pathway under normoglycemic conditions, during hyperglycemia up to 30%

of glucose enters the polyol pathway [7,8]. In addition to fructose generation, flux through the pathway also generates oxidative stress via production of NADH as well as through the competition between aldose reductase (AR) and glutathione reductase for NADPH resulting in decreased glutathione in its reduced form (GSH) [9]. In the periphery, this increased oxidative stress has been implicated in the development of peripheral neuropathy [10], diabetic retinopathy and cataracts [11-14], nephropathy [15], fatty liver [16], macrovascular disease [17] as well as platelet dysfunction [18,19].

In the brain, however, the role of this pathway (either normally or in states of hyperglycemia) remains unclear. In dogs, peripheral glucose infusion increases levels of fructose and sorbitol in the cerebrospinal fluid (CSF) [20,21]. Furthermore, dogs with experimentally induced diabetes have been reported to have 7-10 fold higher CSF fructose levels compared to non-diabetic animals [22,23]. In humans, CSF fructose levels were first reported to be higher than plasma levels in the 1930's [24], an observation later confirmed in the 1960's in a cohort of diabetic and non-diabetic individuals [25]. These studies were, however, limited by the technical inability to precisely measure fructose, the inclusion of both fasting and non-fasting subjects, and the lack of assessment of diabetes control or type of diabetes [25].

With a growing body of individuals exposed to increasing duration of hyperglycemia, understanding the impact of hyperglycemia on the brain is of critical clinical importance. The polyol pathway, through its effects on fructose production as well as oxidative stress, may be a novel mechanism through which glucose exerts its CNS effects.

### 3. Research Plan:

**Aim:** To investigate whether longer-term improvement of glycemic control in poorly controlled diabetes patients with a 12-week intensification of diabetes treatment regimen will lead to decreased polyol pathway activity.

#### Study design:

**Subjects:** 15 T2DM subjects and 15 T1DM subjects with HbA1C > 7.5% will be recruited from Yale New Haven Hospital and the greater New Haven area.

**Inclusion criteria:** Age 18- 65 yrs, BMI  $\geq 18$  kg/m^2, and weight less than 285 pounds (upper limit of scanner),

**Exclusion criteria:** Creatinine > 1.5 mg/dL, Hgb < 10 mg/dL, hematocrit of 37 % for males participants and 33 % for female participants, ALT > 3 x ULN, , untreated thyroid disease, uncontrolled hypertension, known neurological disorders, untreated psychiatric disorders, malignancy, bleeding disorders, current or recent steroid use in last 3 months, illicit drug use; for women: pregnancy, actively seeking pregnancy, or breastfeeding; inability to enter MRI/MRS (per standard MRI safety guidelines).

**Screening visit:** Volunteers will be screened at the YNHH Research Unit (HRU) with a medical history and exam including detailed neurologic exam. Blood tests will be collected for A1C, ALT, TSH, Hematocrit. Less than 35 mL of blood will be drawn for blood work. Women will undergo urine pregnancy testing. Subjects will be required to give us information about their substance use/HIV status because this can affect brain glucose metabolism.

**Intensification of Insulin regimens:** The intensification of the diabetes regimens will be managed by [name], a fully trained attending endocrinologist, and will follow the general strategies outlined in the Position Statement of the American Diabetes Association and the European Association for the Study of Diabetes. All participants will receive exercise and dietary counseling from [name], a nutritionist and registered dietician with extensive

experience with working with individuals with diabetes and obesity. Participants will communicate with a nutritionist regularly over the course of the 12-week study.

All individuals will be asked to perform SMBG at least 4 times a day (before breakfast, lunch, dinner, and bedtime). The daily SMBG records will be sent to [name] weekly for review to guide adjustment of insulin regimens. Target blood glucose levels will be between 80-140 mg/dl before meals and between 100-160 mg/dl at bedtime. Individuals not at goal glycemic targets will undergo intensification of their regimen. Throughout the study, individuals will be contacted via telephone call, email or through additional clinic visits as deemed necessary for maintenance of glycemic control. All individuals will receive education regarding the detection and proper management of hypoglycemia.

**MRI and MRS scanning:**

Subjects will undergo MRS scanning at 4T at 0, and 12 weeks of the study. Scan time is ~45 minutes. After a T1 weighted MRI for anatomy (gray/white/CSF segmentation), glucose and fructose concentrations will be obtained from ~3X3X3 cc voxels. Signals from respective voxels are isolated using a MEGA PRESS-based sequence. Metabolite levels are measured by spectral fitting using a simulated basis set and referenced to total voxel water signal and creatinine to determine concentration.

[figure not shown]
During each of these two scans, plasma glucose, fructose, insulin, HbA1c, and fructosamine levels will be measured concurrently.

A nurse experienced with working in a MRS environment will be with subjects at all times. Vital signs including heart rate and blood pressure will be monitored prior to scanning. If patients express discomfort or anxiety and ask to be removed from the scanner, the session will be immediately terminated.

**Optional Hyperglycemic clamp:**

Prior to MRS scanning at weeks 0 and 12 Subjects may also be invited to participate in an optional overnight admission to normalize blood glucose levels the night before scanning and then a hyperglycemic clamp the following morning.

Subjects will be admitted in the evening prior to MRS scan day (~ 6 PM) to the YNHH research unit, all of their diabetic medications will be held and they will be placed on an insulin drip beginning at 8PM to maintain blood sugar levels at ~90-100 mg/dl until 7AM the next morning. The next morning, participants will be taken to the MRRC for MRS scanning. Following the 45 minute

baseline scan, subjects will remain in the scanner for continuous scanning during the hyperglycemic clamp (see figure). An infusion of 20% dextrose at a variable rate to maintain plasma glucose levels at 220 mg/dL for 4 hours. Glucose infusion rates will be adjusted in response to plasma glucose levels measured every 5-10 minutes. Subjects will be able to take breaks as needed during the 3 hours hyperglycemic clamp and MRS scan. At baseline, 2 and 4 hours, plasma samples will also be obtained for fructose, sorbitol, insulin levels and other hormonal markers.

**Continuous glucose monitoring system (CGMS) and Food logs (at -1, and 11 weeks):** One week prior to the MRS scans at 0 and 12 weeks, subjects will be asked to wear a CGMS (Free style libre) to continuously monitor their interstitial blood glucose levels and record their food intake

**Blood collection for platelet and inflammation analysis:** Participants will also have blood collected (~80 cc) for analysis of polyol pathway activity in platelets as well as for changes in inflammatory markers such as cytokines IL-6, TNF-alpha at weeks 0, and 12 weeks.

**Optional Specimens for Future Storage:** Subjects will be asked to give permission for the storage of any blood obtained during the study that will not be used for the above noted analysis

**4. Genetic Testing** N/A

**5. Subject Population:** Provide a detailed description of the types of human subjects who will be recruited into this study.

15 T2DM subjects with HbA1C > 7.5%

15 T1DM subjects with HbA1C > 7.5%

**6. Subject classification:** Check off all classifications of subjects that will be specifically recruited for enrollment in the research project. Will subjects who may require additional safeguards or other considerations be enrolled in the study? If so, identify the population of subjects requiring special safeguards and provide a justification for their involvement.

- |  |  |  |
|--|--|--|
|  Children              |  Healthy                           |  Fetal material, placenta, or dead fetus |
| X Non-English Speaking                         |  Prisoners                         |  Economically disadvantaged persons      |
|  Decisionally Impaired |  Employees                         |  Pregnant women and/or fetuses           |
|  Yale Students         |  Females of childbearing potential |  |

NOTE: Is this research proposal designed to enroll children who are wards of the state as potential subjects?  Yes  No (If yes, see Instructions section VII #4 for further requirements)

**7. Inclusion/Exclusion Criteria:** What are the criteria used to determine subject inclusion or exclusion?

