**Hyperglycemia clamp:**

The infusion of glucose to achieve hyperglycemia (~220 mg/dl) for 3 hours is not associated with any specific symptoms or significant adverse effects. This modestly high glucose level can be seen in poorly controlled diabetic patients following a meal.

The overnight infusion of insulin to normalize plasma glucose levels is normally not associated with any specific symptoms. There is a small risk that plasma glucose may fall to lower levels resulting in symptoms of hypoglycemia.

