**Phlebotomy:**

Phlebotomy can result in anemia, although the amount of blood taken for these studies should not result in clinically-significant anemia because the blood drawn is spread out over the course of 3 months of participating in the study. Subjects are excluded if hemoglobin < 10 gms/dL or hematocrit of 37 % for males participants and 33 % for female participants.

**10. Minimizing Risks:** Describe the manner in which the above-mentioned risks will be minimized.

General:

- Total blood loss in each subject will be approximately 549 cc over the 3 months of the study if subject completes the entire study (including the optional hyperglycemic clamp portions). Blood draws include: 35 cc at screen, 272 cc at week 0 visit, , and 272 cc at week 12. If the subjects choose not to do the optional hyperclamp portion of the study, the total blood draw will be approximately 202 cc over the course of the study. Blood draws include: 5 cc at screen, 98.5 cc at week 0 visit, , and 98.5 cc at week 12. Subjects with Hgb <10 and hematocrit of 37 % for males participants and 33 % for female participants will be excluded from the study.
- All subjects will be given a telephone number to enable immediate communication with the PI or one of the co-investigators to report any delayed adverse effects.
- Physiological monitoring will be performed during each study.

For glucose infusions:

- Intravenous catheters will be placed under sterile conditions by experienced staff members.
- During glucose infusions, 20% dextrose is used reducing the risk of thrombophlebitis normally associated with the use of excessively hypertonic glucose solutions.
- To avoid hypoglycemia during the overnight insulin infusions, plasma glucose will be monitored closely using a bedside glucose analyzer (YSI). This will involve plasma measurements every 30 minutes and at more frequent intervals if plasma glucose is low (less than 4 mM, 70 mg/dl).
- All studies will be performed under the direct supervision of a physician.
- All solutions for infusion will be pyrogen free and prepared in a sterile environment.

12-week Intensification of Diabetes Regimen:

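### The optional hyperglycemic clamp is given as 4 hours and as 3 hours in the same paragraph, and the risk statement describes 3 hours only

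*Combined protocol and SAP*

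**What the plan says.** All references are to the combined protocol and SAP.

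- **Section V, 3. Research Plan, Optional Hyperglycemic clamp, infusion sentence:** "An infusion of 20% dextrose at a variable rate to maintain plasma glucose levels at 220 mg/dL for 4 hours".
- **Same paragraph, sentence on breaks:** "Subjects will be able to take breaks as needed during the 3 hours hyperglycemic clamp and MRS scan".
- **Same paragraph, sampling sentence:** "At baseline, 2 and 4 hours, plasma samples will also be obtained" (for fructose, sorbitol, insulin and other hormones).
- **Section V, 9. Risks, Hyperglycemia clamp:** "The infusion of glucose to achieve hyperglycemia (~220 mg/dl) for 3 hours is not associated with any specific symptoms".
- **Section V, 3, MRI and MRS scanning:** "Scan time is ~45 minutes". The clamp paragraph puts this baseline scan before the clamp, with scanning continuing through the clamp. It refers to a figure that is not reproduced in the text available.
- **Section V, 12. Statistical Considerations:** primary endpoint (c) is brain intracellular fructose and glutathione after the clamp, at weeks 0 and 12.

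No other section gives a clamp duration that settles the matter.

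**The concern.** Clamp duration is an operating figure. It fixes how long a participant is held at about 220 mg/dL and how long the session in the scanner runs. It also decides what the risk section has to cover. And it defines the glucose stimulus behind endpoint (c), which supports the hypothesis that fructose production in response to the clamp falls after 12 weeks of better control.

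With two durations in the text, one of two things is wrong. Either the risk section describes a shorter exposure than participants undergo, or the sampling schedule contains a time point that lies beyond the clamp. The investigator rates the study as greater than minimal risk, so the risk section should describe the procedure as it will be performed.

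**Working it through.** This is a comparison of text plus simple addition. No power, alpha or sample-size figure is involved.

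**Inputs**

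| Item | Value | Source |
|---|---|---|
| Duration in the infusion sentence | 4 h = 240 min | Optional Hyperglycemic clamp |
| Duration in the breaks sentence | 3 h = 180 min | same paragraph |
| Duration in the risk statement | 3 h = 180 min | Section V, 9. Risks |
| Baseline scan | about 45 min | MRI and MRS scanning; clamp paragraph |
| Last plasma sample | 4 h = 240 min | Optional Hyperglycemic clamp |
| Clamps per participant | up to 2 (weeks 0 and 12) | Optional Hyperglycemic clamp |

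**Step 1. Can the baseline scan reconcile the two durations?**

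- Suppose 3 hours means scan plus clamp. The clamp is then 180 − 45 = 135 min (2 h 15 min). That equals neither the 240 min of the infusion sentence nor the 180 min of the risk statement.
- Suppose 4 hours means the whole session with a 3-hour clamp. Then 45 + 180 = 225 min (3 h 45 min), which is near 240 min. But the infusion sentence attaches its 4 hours to holding glucose at 220 mg/dL, and that begins only after the baseline scan.
- With a 4-hour clamp the session is 45 + 240 = 285 min (4 h 45 min), so 3 hours cannot be the combined time either.

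None of these readings makes the sentences agree.

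**Step 2. If the clamp lasts 4 hours**

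- Exposure beyond the risk statement, per clamp: 240 − 180 = 60 min.
- As a share of the clamp: 60/240 = 25%.
- Over two clamps: 2 × 1 h = 2 h out of 2 × 4 h = 8 h.

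**Step 3. If the clamp lasts 3 hours**

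- Last plasma sample minus clamp end, with the clock started at clamp start: 240 − 180 = +60 min. The sample would be a post-clamp sample, and the text does not describe it as one.
- The 4 hours in the infusion sentence would remain unexplained.

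Step 3 takes sampling time from clamp start, the natural reading because the sampling sentence follows the infusion instruction in the clamp paragraph. All steps ignore breaks and any gap between scan and clamp.

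**The case against.** The strongest reply is that the conflict is lopsided. The 4 hours stands in the sentence that directs the infusion, and the 2- and 4-hour samples fit it. The 3 hours appears in a sentence whose purpose is to allow breaks, and in a risk narrative that instructs nobody. This is a fair account of how the sentences differ in function. It does not remove the conflict, because the risk section still describes a shorter exposure than the infusion sentence. Nor does it settle which duration is intended.

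The reply is also right that 25% measures wording and not harm. The risk section argues mainly from the glucose level: "This modestly high glucose level can be seen in poorly controlled diabetic patients following a meal". Section V, 10. Minimizing Risks adds "All studies will be performed under the direct supervision of a physician" and physiological monitoring, neither with a time limit. A reader might infer that a fourth hour would be unsupervised or unsafe; the documents do not support that.

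A reader might also infer that the mismatch biases endpoint (c). That does not follow:

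- Endpoint (c) comes from MRS, and scanning continues through the clamp. The plasma sampling times do not time it.
- Nothing suggests that duration would differ between weeks 0 and 12.

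Finally, a reader might go on to fault the plan for not stating a time zero or an MRS reading window. The clamp paragraph refers to a figure that may give this timing, so no such omission can be claimed. Timing the samples from the start of the baseline scan is a further possible reading, but no sentence supports that clock.

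**Conclusion.** The contradiction is real and should be corrected before the protocol is used. Its size is 60 minutes per clamp. That is either one hour in four outside the risk statement, or a last plasma sample one hour after the clamp has ended. The first figure follows directly from the text; the second assumes sampling is timed from clamp start.

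Its reach is limited. The clamp is optional, total enrollment is 30, endpoints (a) and (b) do not depend on it, and Section V, 12 describes the work as exploratory. What is established is an inconsistent operating figure and a risk statement that may not match the procedure. No bias in endpoint (c), no lapse in supervision and no missing timing information is established. The figure that is not shown might indicate the intended duration, but it would not make the conflicting sentences agree. Which duration is right is not judged here.

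**What to change.** 1. Reconcile the infusion sentence, the breaks sentence and the risk statement to one clamp duration. The choice is the investigator's.
2. Make the last plasma sampling time consistent with that duration.
3. State that the same duration applies at weeks 0 and 12, because endpoint (c) compares the two clamps.
4. Check the consent text, which was not available for this review, and bring it into line if it differs.

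The cost is a few words in the clamp paragraph and in Section V, 9, with no added visit, procedure or sample. If the consent text has to change, that edit needs IRB review.

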**Inclusion Criteria:**

15 Type 2 DM subjects with HbA1C > 7.5%

15 Type 1 DM subjects with HbA1C > 7.5%

Age 18- 65

BMI  $\geq$ 18 kg/m^2

Weight  $\leq$  285 pounds

**Exclusion criteria:** Creatinine > 1.5 mg/dL, Hgb < 10 mg/dL, hematocrit of 37 % for males participants and 33 % for female participants ,ALT >3 x ULN, untreated thyroid disease, uncontrolled hypertension, known neurological disorders, untreated psychiatric disorders, malignancy, bleeding disorders, current or recent steroid use in last 3 months, illicit drug use; for

women: pregnancy, actively seeking pregnancy, or breastfeeding; inability to enter MRI/MRS (as per standard MRI safety guidelines).

8. How will **eligibility** be determined, and by whom?

Eligibility will be determined by a qualified physician associated with the research protocol and will be based upon the above inclusion/exclusion criteria

9. **Risks:** Describe the reasonably foreseeable risks, including risks to subject privacy, discomforts, or inconveniences associated with subjects participating in the research.

**Hyperglycemia clamp:**

The infusion of glucose to achieve hyperglycemia (~220 mg/dl) for 3 hours is not associated with any specific symptoms or significant adverse effects. This modestly high glucose level can be seen in poorly controlled diabetic patients following a meal.

The overnight infusion of insulin to normalize plasma glucose levels is normally not associated with any specific symptoms. There is a small risk that plasma glucose may fall to lower levels resulting in symptoms of hypoglycemia.

**MRI/MRS:**

The major risk is the possibility of metal flying into the magnet. Subjects are asked to fill out a detailed MRI safety screening questionnaire (from the MRRC) to determine whether there are any contraindications to entering the magnet. Furthermore, subjects and all personnel are scanned with a metal detector before entering the magnet area and all metal objects are removed. Subjects with metal implants that cannot be safely removed, or pacemakers are not admitted to this study. Some subjects feel claustrophobic or experience physical discomfort inside the scanner. Communication is set up so that the subjects can talk to the investigators and may be removed from the scanner if they are uncomfortable. A RN will be present inside the scanner at all times with the subject.

**CGMS:**

The CGMS poses no major risks to the subjects. Participants may feel a mild discomfort (pin prick sensation) during the sensor insertion. Some individuals may experience black and blueness of the skin at the insertion site of the CGMS sensor, which resolves by itself in a few days. Redness and discomfort (inflammation) can occur at the sensor insertion site. Rarely sensors may fracture, and a small piece may remain under the skin which will need to be removed by the physician. This may cause mild discomfort, bruising, or temporary bleeding.

**12-week Intensification of Diabetes Regimen:**

The 12-week intensification of diabetes management poses minimal risks to the patient. All medical management strategies will follow the general strategies outlined in the Position Statement of the American Diabetes Association and the European Association for the Study of Diabetes [48]. There may be slightly increased risk of hypoglycemia with improved glycemic control; however, as patients are all poorly controlled T2DM patients and we are targeting blood glucose levels to between 80-140 mg/dl before meals and between 100-160 mg/dl at bedtime, we expect that this risk will be minimal. In fact, participants may benefit from the free supplies and increased frequency of medical attention to lower their blood glucose into target ranges.

